# 1 General Information

## 1.1 Synopsis

Title:	Biomarker-guided implementation of angiotensin-II (AT-II) to reduce the occurrence of kidney damage after cardiac surgery
Short Title:	Aided-Trial
Sponsor's Study Code:	WWU20_0016
EudraCT-No.:	2021-003088-87
Sponsor:	Westfälische Wilhelms-Universität Münster
Investigator:	Univ.-[name]. med. [name]
Indication:	Cardiac surgical patients at high risk for AKI
Study Design:	Single-centre clinical Trial Two-arm, randomised, blinded, controlled, parallel-group trial
Investigational Medicinal Product:	Test product: Angiotensin II acetat (Giapreza 2,5 mg/ml) Reference therapy: Placebo (0.9 % NaCl)
Therapy	
After identifying cardiac surgery patients at high risk for AKI by renin levels (<math>\Delta</math>-renin (difference between post- and pre-operation) <math>\geq</math> 3.7 <math>\mu</math>U/ml 4h after CPB) who require vasopressors, patients will be randomly allocated to the control or intervention group.
 
Experimental intervention: Angiotensin II will be added to the first-line vasopressor (norepinephrine) and the angiotensin II dose and norepinephrine will be adjusted so that the mean arterial pressure is above 65 mmHg and the first-line vasopressor (norepinephrine) can completely be weaned..
 
Control intervention: The control substance (0.9% NaCl) will be added to the first-line vasopressor (norepinephrine) and the dose of the control substance and norepinephrine will be adjusted so that the mean arterial pressure is above 65 mmHg.
 
The treatment with study medication will be performed for 12 hours. If the patient requires a vasopressor after the intervention period, the first-line vasopressor (norepinephrine) is administered..

Objectives:	
The primary objective of this trial is to investigate the efficacy of AT-II vs. standard of care on the biomarkers [TIMP-2]*[IGFBP7] in high-risk patients undergoing cardiac surgery.
 
HYPOTHESIS: Superiority of AT-II in cardiac surgery patient with a hyperreninemia and vasopressor use compared to standard of care with respect to kidney damage (personalized approach).

Endpoints:	
Primary Endpoint:
 

• kidney damage after cardiac surgery identified by the difference between [TIMP-2]*[IGFBP7] levels 12h after

	
randomization and [TIMP-2]*[IGFBP7] levels at randomization
 
Secondary Endpoints:
 
 
• occurrence of AKI within 72h after cardiac surgery (according to the KDIGO criteria)
 
• occurrence of moderate and severe AKI within 72h after cardiac surgery (according to the KDIGO stage 2 and 3)
 
• amount of volume application
 
• transient (<72h) and persistent (<72h) AKI
 
• fluid status
 
• dose and duration of vasopressor use
 
• creatinine clearance on day one after cardiac surgery
 
• free-days through day 28 of vasoactive medications and mechanical ventilation
 
• renal recovery at day 90 (renal recovery is defined as serum creatinine levels < 0.5 mg/dl higher than baseline serum creatinine (creatinine level before surgery)
 
• 30-day, 60-day and 90-day mortality
 
• length of ICU stay
 
• length of hospital stay
 
• use and duration of renal replacement therapy within hospital stay
 
• use of RRT at days 30, 60, 90
 
• MAKE90 (major adverse kidney events consisting of mortality, dialysis dependency, persistent renal dysfunction (defined as serum creatinine <math>\geq</math> 2x compared to baseline value) at day 90
 
• Effect of ACEi/ARBs use on the AT II effect
 
• Correlation between the severity of hyperreninemia and the AT II effect
 
 
Other variables:
 
 
• Surveillance of vital parameters on ICU
 
• Safety laboratory parameters
 
• Occurrence of thromboembolism
 
• Adverse events
 
 
Add-on study:
 
 
• determination of further biomarkers (e.g. KIM-1, chitinase, NGAL, hyaluronic acid) and anti- and pro-inflammatory mediators (IL-6, IL-10...)
 

Planned Number of Study Centers:	1
Number of Patients/ Sample size:	Expected [TIMP-2]*[IGFBP7] level in the control group: median=0.84, Q1=0.35, Q3=1.57 and in the AT-II group: median=0.58, Q1=0.26, Q3=1.20 (based on Meersch et al., Intensive Care Med 2017). A total number of 64 patients will be recruited and a number of 32 patients will be randomized to each of the two treatment arms. With an expected 5% dropout rate, up to 2 patients per treatment arm will be non-evaluable. With a number of n=30 evaluable patients per treatment arm, the location shift between the distributions of the biomarker [TIMP-2]*[IGFBP7] in the AT-II and the control group can be

	estimated with an expected precision $\pm 0.35\text{ng/ml}^2/1000$ (half-width of the 95% confidence interval).
Inclusion Criteria:	
Inclusion criteria for registration
 
 
1. Adult patients scheduled for cardiac surgery with cardiopulmonary bypass (CPB),
 
2. 18 years of age or older,
 
3. cardiac index <math>> 2.1 \text{ l/min per square meter}</math>,
 
4. Written informed consent.
 
 
Inclusion criteria for randomization
 
Registered patients will be randomized only if
 
 
1. <math>\Delta</math>-renin (difference between post- and pre-operation) <math>\geq 3.7 \mu\text{U/ml}</math> 4h after CPB.
 
2. postoperative hypotension requiring vasopressors
 

Exclusion Criteria:	
 
1. Preexisting AKI (stage 1 and higher)
 
2. Patients with cardiac assist devices (ECMO, LVAD, RVAD, IABP)
 
3. Pregnant women, breastfeeding women and women of childbearing potential
 
4. Known (Glomerulo-) Nephritis, interstitial nephritis or vasculitis
 
5. Chronic kidney disease with eGFR <math>< 20 \text{ ml/min/1.73m}^2</math>
 
6. Dialysis dependent CKD
 
7. Prior kidney transplant within the last 12 months
 
8. Emergency surgery in the context of an acute coronary syndrome
 
9. Hypersensitivity to the active substance, or to any of the excipients of the study medication
 
10. Bronchospasm
 
11. Liver failure
 
12. Mesenteric ischemia
 
13. Participation in another intervention trial in the past 3 months
 
14. Persons with any kind of dependency on the investigator or employed by the institution responsible or investigator
 
15. Persons held in an institution by legal or official order
 

Visits:	
Screening: T1: Screening T2: Surgery until 4h after terminating CPB
 
Treatment: T3: Operation Day
 
Observation: T4: POD 1 T5: POD 2 T6: POD 3 T7: POD 7/Discharge T8: Follow-up POD 30 T9: Follow-up POD 60 T10: Follow-up POD 90

Statistical Methods	
Efficacy:
 
The randomized groups will be descriptively compared on all baseline variables using summary statistics such as mean and standard deviation, median and quartiles, or frequency and percentage, as appropriate. In inferential statistical analyses two-sided significance tests will be applied with a local

	
significance level alpha=0.05. All point estimates of parameters of interest will be supplemented by 95% confidence intervals unless otherwise stated. SAS or SPSS statistical software will be used for all data analyses.
 
Description of the primary efficacy / test accuracy analysis and population:
 
The primary efficacy analysis will include all randomized subjects (full analysis set) and will be performed according to the intention-to-treat principle, i.e. all subjects are analyzed in the group to which they were randomized. Additional sensitivity analyses will be performed according to the per-protocol principle. The effect of AT-II versus placebo on the biomarker [TIMP-2]*[IGFBP7] will be estimated with a non-parametric 95% confidence interval of the location shift between the distributions of the biomarker [TIMP-2]*[IGFBP7] in the AT-II and the placebo group, respectively.
 
Safety:
 
Safety data will be evaluated descriptively, including all recruited study patients who received at least one dose of study therapy (safety population). Results are reported by mean parameter estimates and associated 95% confidence intervals.
 
Secondary endpoints:
 
Statistical analysis of the pre-specified secondary endpoints will be performed with descriptive and inferential statistical methods.

Financial Support:	The project is supported by the DFG
Schedule	
Planned start date of the study (FPFV): 01.10.2021      Planned end date of recruitment (LPFV): 15.04.2022      Planned end date of the study (LPLV): 15.07.2022
 
Planned recruitment duration: 6,5 months      Duration of single patient participation: 90 days      Planned overall duration of the study: 9,5 months

## 1.2 Flow Chart

Visit	T1 S 	T2 R  B 		T3 OD	T4-T6 POD 1-3	T7 Dis-charge /POD 7	T8 POD 30	T9 POD 60	T10 POD 90
Informed Consent	X								
Inclusion and Exclusion criteria	X								
Renin measurement before and after cardiac surgery (4 hours after cardiopulmonary bypass)			X	X					
Registration		X							
Demographic data Age, sex, BMI, comorbidities (EuroSCORE, hypertension, coronary artery disease, congestive heart failure, NYHA, peripheral vascular disease, diabetes, previous stroke or transient ischemic attack, chronic liver disease, chronic kidney disease, chronic obstructive pulmonary disease, cancer), medication (b-blockers, ACEi/ARBs, diuretics, anticoagulation)			X						
Admission diagnosis, Category of admission (elective, emergency)			X						
Surgical parameters nature of surgical procedure, duration of surgical procedure, duration of CPB, duration of aortic cross clamp				X					
Randomization				X					
Urinary [TIMP-2]*[IGFBP] measurement At randomization and 12 h after start of intervention				X					
Intervention / Study medication				X					
APACHE II				X					
Hemodynamics (MAP, HR, CVP)				X	X				
Pressors				X	X				
SOFA-Score				X	X				
KDIGO criteria					X				
Fluid balance / 24h urine volume				X	X				
Concomitant Medication N-acetylcysteine, amphotericin, aminoglycosides, cyclosporine, tacrolimus, radiocontrast agents, diuretics				X	X				
Safety laboratory test Complete blood count, potassium-, sodium-, creatinine and BUN and eGFR, pH, bicarbonate, bilirubin, CRP, PCT, coagulation parameter		X			X				
Add-on study				X 	X 				
Mortality						X	X	X	X
Length of stay (ICU, Hospital)						X		X	
Duration of ventilator support / duration of administration of vasopressors						X	X		
Number of days of RRT/RRT dependence						X			X
(Serious) adverse events				X	X	X	X	X	X

 Screening

 Registration

 Baseline ( prior operation until randomization)

 Blood and urine samples will be collected 4h after CPB, 12h and 24h after start of study medication

 Blood samples will be collected on POD 2 and 3

### 1.3 Abbreviations

ADL	Activities of Daily Living
AE	Adverse Event
AMG	Arzneimittelgesetz
AKI	Acute Kidney Injury
BfArM	Federal Institute for Drugs and Medical Devices (Bundesinstitut für Arzneimittel und Medizinprodukte)
CKD	Chronic kidney disease
CRRT	Continuous Renal Replacement Therapy
CRF	Case Report Form
CTCAE	Common Terminology Criteria for Adverse Events
DMC	Data Monitoring Committee
DSUR	Development Safety Updat Report
ICU	Intensive Care Unit
eCRF	Electronic Case Report Form
FPFV	First patient first visit
GCP	Good Clinical Practice
ICH	International Conference on Harmonisation of Technical Requirements for Registration of Pharmaceuticals for Human Use
IMP	Investigational Medicinal Product
ISF	Investigator Site File
KDIGO	Kidney Disease: Improving Global Outcomes
ZKS	Zentrum für Klinische Studien
LPFV	Last patient first visit
LPLV	Last patient last visit
NA	Not applicable
ND	Not done
OD	Operative day
POD	postoperative day
RAAS	Renin-angiotensin-aldosterone system
RRT	Renal Replacement Therapy
SAE	Serious Adverse Event
SAR	Serious Adverse Reaction
SAS	Statistical Analysis System
SOFA	Sequential Organ Failure Assessment
SOP	Standard Operating Procedure
SUSAR	Suspected Unexpected Serious Adverse Reaction
TMF	Trial Master File

## 2 Introduction

Vasoplegic syndrome is a form of distributive shock that is characterized by low arterial pressure with reduced systemic vascular resistance and normal or elevated cardiac output[1] that occurs in 5 to 25% of patients undergoing cardiac surgery. Patients with vasoplegia after cardiac surgery are at higher risk of organ failure, including acute kidney injury (AKI)[2, 3]. Postsurgical AKI is associated with several adverse outcomes. Attempts to prevent AKI have largely been futile so far. Prior studies often started with the interventions after an AKI event, when a decline of kidney function (i.e. glomerular filtration rate) was already established. Application of norepinephrine is currently considered as the first-line therapy for vasoplegia, but all catecholamines have adverse effects, including myocardial ischemia and arrhythmias[4]. In a recent observational trial, we demonstrated that there is a dysregulation in the renin-angiotensin-aldosterone system (RAAS) likely caused by a reduced angiotensin-converting enzyme (ACE) activity after cardiac surgery. Elevated renin levels identified patients at risk for AKI and were associated with cardiovascular instability and increased AKI rate after cardiac surgery[5]. Furthermore, elevated renin levels could be used to identify high-risk patients for cardiovascular instability and AKI who would benefit from timely intervention with angiotensin II (AT-II) that could improve their outcomes[5]. Therefore, the application of AT-II to treat a postoperative hypotension would mean a hormone substitution. We hypothesize that the application of AT-II added to standard of care in cardiac surgery patients with a high risk for AKI as identified by AKI biomarkers reduces kidney damage.

### 2.1 Background Information and Rationale

Acute kidney injury (AKI) can be defined by changes of serum creatinine and/or urine output, according to the KDIGO criteria[6]. In cardiac surgery patients, the AKI rate is up to 30%, with 1–2% of patients requiring renal replacement therapy (RRT)[7-9]. Cardiac-surgery associated AKI (CSA-AKI) is associated with increased short- and long-term morbidity and mortality as well as increasing hospital costs[7-9].

Shock after cardiac surgery is associated with increased mortality[10, 11]. Cardiopulmonary bypass (CPB) represents a common clinical setting of sympathetic nervous system activation and cardiovascular instability. Vasoplegia is a form of distributive shock that is characterized by low arterial pressure with reduced systemic vascular resistance and normal or elevated cardiac output[1]. It occurs in 5 to 25% of patients undergoing cardiac surgery. Patients with vasoplegia after cardiac surgery are at higher risk of organ failure, including AKI, and have an increased mortality rate and longer hospital length of stay[2, 3].

Application of norepinephrine is currently considered as the first-line therapy for vasoplegia but all catecholamines have adverse effects, including myocardial ischemia and arrhythmias[4]. In addition, in vasoplegic states, vascular smooth muscle cells may become unresponsive to catecholamines. The underlying mechanisms are complex and include adrenoceptor desensitization, increased nitric oxide synthesis, activation of adenosine triphosphate-sensitive K+ channels, and vasopressin and corticosteroid deficiency[12].

The renin-angiotensin-aldosterone system (RAAS) is a hormone system that plays a central role in regulating blood pressure and fluid, glomerular filtration rate, and electrolyte balance[13, 14]. Renin, a proteolytic enzyme released by juxtaglomerular cells in response to hypotension, decreases sodium delivery to the distal tubule, activates the sympathetic nerve system, and cleaves angiotensinogen to angiotensin (AT)-I which is a precursor of the vasoactive AT-II. The RAAS system is regulated by a biofeedback loop. AT-II generation inhibits renin release, whereas renin levels increase when there is insufficient activation of the AT-II type 1 receptor. Administration of Angiotensin Converting Enzyme (ACE) inhibitors and AT-II receptor blockers and reduced AT-II generation cause a corresponding increase in renin levels.[15, 16]

Despite numerous clinical trials using several interventions, [17] a reliable means to prevent AKI remains elusive. Clinical trials focusing on septic patients suggest that AT-II is a potent vasopressor. However, no human data exist whether the application of AT-II in high-risk

patients identified by renin levels (individualized approach) reduces kidney damage and improves kidney function after cardiac surgery. Furthermore, leukocyte function and mediators modulating inflammation will be investigated in an add-on study.

## 2.2 Risk-Benefit Analysis

Patients included in this trial are at high risk for AKI. Currently, there is no pharmacologic option available to prevent the development of AKI. However, it is well known that AKI is associated with an 8-fold increased risk for the development of chronic kidney disease (CKD) as well as end-stage renal disease and an increased risk for mortality.

AT-II is a synthetic peptide hormone which is approved for refractory hypotonia in adults in septic or other forms of distributive shock. Vasoplegia, the clinical condition treated in this clinical trial, is a form of distributive shock. Preliminary data have shown that treatment with AT-II reduced hyperreninemia in cardiac surgical patients with vasoplegia. As hyperreninemia is supposed to be associated with AKI [5], it is conceivable that a treatment of AT-II reduces kidney damage. Known interactions or side effects of AT-II are limited to thromboembolic complications. Therefore, patients with any form of prothrombotic conditions will not be included in this trial. Moreover, patients with hypersensitivity to the active substance, or to any of the excipients of the study medication will be excluded from the trial. The application of AT-II will be gradually decreased since patients may experience hypotension or worsening of the underlying diagnosis of shock on abrupt withdrawal or premature discontinuation if complications occur that might be related to the use of AT-II. The burdens and predictable risks will be closely supervised by the treating physicians. To mitigate the risk of thromboembolic events in the clinical trial laboratory tests of coagulation (e.g. PTT, INR, Thrombocytes and – if applicable antifactor Xa are implemented to detect and treat hypercoagulation during the treatment period (see 8.4.3 Rescue Medication and Emergency Measures). Furthermore – depending on the operation and the previous illnesses – all patients are started with at least prophylactic anticoagulation on the first evening.

Patients assigned to the control group receive only standard care and may not have a treatment benefit. However, since a renoprotective effect is still unknown, patients participating in the trial have the same risks as not participating in the trial. Patients with vasoplegia receive vasopressors in order to increase the systemic vascular resistance (SVR) and subsequently the mean arterial blood pressure (MAP). This ensures organ perfusion and oxygen delivery. Norepinephrine is currently the first-line treatment to treat vasoplegia induced by different causes. However, other vasopressors are also available which can increase the SVR and MAP. Although the available vasopressors (norepinephrine, vasopressin, angiotensin II) have different mode of actions, they are all used to secure organ perfusion. As both groups (intervention group and control group) have the same MAP target, leaving out norepinephrine and replacing it by another vasopressor is without an increased risk for the patient.

This trial may result in a substantial improvement in the management of patients at risk of AKI with a potential improvement of patients' outcome. A participation in this trial will not influence the therapeutic treatment of patients after cardiac surgery. All patients receive standard treatment according to the current standards.

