#### 5.2.2 Exclusion Criteria

1. Preexisting AKI (stage 1 and higher)

2. Patients with cardiac assist devices (ECMO, LVAD, RVAD, IABP)
3. Pregnant women, nursing women and women of childbearing potential
4. Known (Glomerulo-) Nephritis, interstitial nephritis or vasculitis
5. CKD with eGFR < 30 ml/min
6. Dialysis dependent CKD
7. Prior kidney transplant within the last 12 months
8. Emergency surgery in the context of an acute coronary syndrome
9. Hypersensitivity to the active substance, or to any of the excipients of the study medication
10. Bronchospasm
11. Liver failure
12. Mesenteric ischemia
13. Participation in another intervention trial in the past 3 months
14. Persons with any kind of dependency on the investigator or employed by the institution responsible or investigator
15. Persons held in an institution by legal or official order

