## 6 Patient Inclusion, Registration and Randomization

Patients who are cared for at the study sites and who are possibly eligible will be invited for study participation until the desired number of patients is achieved. Once written informed consent for participation has been given (cf. section 15.215.2), a subject identification code will be assigned.

After successful registration, when patients meet all designated inclusion criteria (including identifying a high risk patient ( $\Delta$ -renin (difference between post- and pre-operation)  $\geq 3.7 \mu\text{U/ml}$  4 h after CPB), and none of the exclusion criteria, patients will be randomized using an internet-based randomization tool at <https://www.randomizer.at>. Randomization will be performed in a proportion of 1:1.

The time interval between patient fulfilling eligibility criteria and start of infusion may not exceed 30 minutes.

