### **8.5 Pregnancy, Breast Feeding and Fathering of a Child**

As there is currently insufficient data on administration of GIAPREZA to pregnant women, nursing mothers and children, administration of GIAPREZA is not recommended.

This study does not include pregnant women. For women of childbearing potential, a pregnancy test must be performed before inclusion in the clinical trial. Inclusion in the clinical trial is not possible if the test result is positive.

Breastfeeding women are also not included in the study.

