## 9 Study Conduct and Study Assessments

### 9.1 Screening (and Baseline) Visit

All patients scheduled for cardiac surgery with CPB will be documented in a screening log. If a patient fulfills all inclusion criteria and does not have any exclusion criteria ("eligible"), it should be documented in the screening log whether inclusion in the clinical trial has occurred. If the patient is not included in the clinical trial, the cause should be documented in the screening log.

A patient must provide written consent before undergoing any protocol-required assessments.

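### Eligibility rules contradict each other: the prothrombotic exclusion promised in section 2.2 is in neither exclusion list, and the CKD cut-off is eGFR 20 in the synopsis but 30 in section 5.2.2

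*Protocol*

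**What the plan says.** **Prothrombotic conditions.** Section 2.2 (Risk-Benefit Analysis) names thromboembolic complications as the known risk of angiotensin II and draws the consequence that "patients with any form of prothrombotic conditions will not be included in this trial". It then announces a second exclusion: "patients with hypersensitivity to the active substance, or to any of the excipients of the study medication will be excluded from the trial".

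**How eligibility is decided.** Section 9.1 calls a patient eligible by this rule: "If a patient fulfills all inclusion criteria and does not have any exclusion criteria". Section 6 randomises registered patients who meet all the inclusion criteria "and none of the exclusion criteria, patients will be randomized using an internet-based randomization tool". Neither section names another source of exclusions.

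**Kidney function.** Exclusion item 5 in the synopsis (section 1.1) begins "Chronic kidney disease with eGFR" and sets the limit at below 20 ml/min/1.73m². Item 5 in section 5.2.2 reads "CKD with eGFR < 30 ml/min".

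**Childbearing potential.** Item 3 in section 5.2.2 excludes "Pregnant women, nursing women and women of childbearing potential", and the synopsis has an equivalent item. Section 8.5 asks for a pregnancy test in women of childbearing potential before they enter the trial and adds: "Inclusion in the clinical trial is not possible if the test result is positive".

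**The concern.** An exclusion protects patients only if the people who screen and randomise apply it. Section 2.2 counts the prothrombotic exclusion among its reasons why the risk is acceptable, yet the lists to which sections 6 and 9.1 tie the decision do not contain it. A patient with a prothrombotic condition can satisfy every listed criterion and be randomised. The protocol's own figures show that the risk is not trivial: venous thromboembolism in 6.1% against 0% on placebo (section 7.1.3), and thromboembolic events in 12.9% against 5.1% (section 7.1.5).

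The two eGFR limits have a similar effect: two people who follow the protocol exactly can reach opposite decisions on the same patient. The primary endpoint is a kidney-damage biomarker and many secondary endpoints are renal, so baseline kidney function is central to who is being studied. At stake are the safeguard itself, the population to which the result applies, and the standard for judging whether a patient was wrongly enrolled. Section 11.3.1 judges that against the inclusion and exclusion criteria.

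**Working it through.** The protocol gives no figure to reproduce here. The check is a comparison of passages, plus one unit conversion.

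**1. Exclusions announced in section 2.2 against the lists**

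| Announced in 2.2 | Synopsis (15 items) | Section 5.2.2 (15 items) | Inclusion criteria |
|---|---|---|---|
| Hypersensitivity | item 9 | item 9 | – |
| Prothrombotic conditions | absent (0 of 15) | absent (0 of 15) | absent |

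One of the two announced exclusions was carried over. The nearest vascular item, mesenteric ischemia (item 12 in both lists), is not equivalent. Because the hypersensitivity exclusion does appear in both lists, the lists evidently are meant to hold the exclusions that 2.2 announces.

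Section 8.4.3 sets separate anticoagulation targets for patients with a higher risk profile. It does not define that phrase, so it does not show whether patients with prothrombotic conditions are expected in the trial, and it does not resolve the conflict.

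**2. The CKD limit**

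| Source | Excluded if eGFR is below | Unit stated |
|---|---|---|
| Synopsis, item 5 | 20 | ml/min/1.73m² |
| Section 5.2.2, item 5 | 30 | ml/min |

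If both are read as indexed to body surface area, the lists disagree for every non-dialysis CKD patient with 20 ≤ eGFR < 30. Dialysis-dependent patients are excluded by item 6 in both lists and are not affected.

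If section 5.2.2 is read literally as not indexed, its limit on the synopsis scale is 30 × 1.73 / BSA = 51.9 / BSA. The protocol gives no body surface areas, so these are assumed values:

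- BSA 1.6 m²: 51.9 / 1.6 = 32.4 ml/min/1.73m²
- BSA 1.73 m²: 51.9 / 1.73 = 30.0
- BSA 2.0 m²: 51.9 / 2.0 = 26.0 (rounded from 25.95)
- BSA 2.2 m²: 51.9 / 2.2 = 23.6

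On that reading the lower end of the conflict stays at 20 and the upper end moves between about 23.6 and 32.4 with body size. The two limits do not coincide at any of these values.

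**3. Childbearing potential**

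Criterion 3 excludes these women outright. Section 8.5 tests them before inclusion and names only a positive result as a bar. If criterion 3 is applied, the test has no one to select. If the test is meant to select, criterion 3 is too wide.

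**4. What the statistics inherit**

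The primary analysis in section 12 covers all randomised patients by intention to treat, with 1:1 allocation. Ambiguous eligibility acts before randomisation and so affects both arms alike; it does not bias the comparison. It does affect the description of the population and any per-protocol sensitivity analysis that uses eligibility.

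**The case against.** The best counter-arguments are these.

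- *Section 2.2 is itself binding.* Section 15.5 obliges the investigator to follow the protocol, and 2.2 is part of it. This is true, but it does not help: it binds the investigator both to a text that excludes these patients and to sections 6 and 9.1, which let them through. It gives no precedence between 20 and 30 either.
- *Other safeguards exist.* Coagulation tests, at least prophylactic anticoagulation for all patients (2.2), anticoagulation targets (8.4.3) and regular Data Monitoring Committee review (10.3) are all planned. These stand as mitigation. However, 2.2 presents the tests and anticoagulation in addition to the exclusion, not in its place.
- *The trial has one centre, so practice will not vary between sites.* This limits inconsistent application. It does not tell the one site which rule to use.
- *The missing body-surface suffix in 5.2.2 is probably an omission.* This is the simpler reading, since the synopsis and the KDIGO table in section 18.2 both give eGFR per 1.73 m². The main conflict is then 20 to below 30, and the converted range is only a bound for the literal reading.
- *The per-protocol set may be defined in the SAP.* Accepted. The protocol does not tie that set to eligibility, so the effect there is conditional and is not the basis of the point.
- *Criterion 3 and section 8.5 can both be obeyed.* Also accepted: the test would merely be redundant. This part is editorial.

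None of these removes the two main contradictions.

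**Conclusion.** The point holds. The current text contradicts itself on two eligibility rules that matter. The prothrombotic exclusion on which section 2.2 relies has no counterpart among the 15 items of either list or among the inclusion criteria. The CKD limit differs between the lists, so that eGFR from 20 to below 30 is decided in opposite ways, assuming both units are meant as indexed. The childbearing-potential wording is a minor mismatch.

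The number of patients concerned cannot be derived from the protocol; each one randomised would be 1 of 64, or 1.6%. The primary intention-to-treat comparison, the sample size and the precision statement are not affected. The weight of the point comes from the safety safeguard and from the lack of a single rule for who belongs in the trial. A statistical analysis plan cannot repair this, because eligibility is set in the protocol. No view is taken here on which threshold or exclusion is clinically right.

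**What to change.** Reconcile the passages by amendment:

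1. Either carry the exclusion stated in section 2.2 into both the synopsis and section 5.2.2, or remove it from 2.2 and revise the risk-benefit argument without it. If it is carried over, give it a definition that can be checked at screening, because the present phrase is undefined.
2. State one eGFR limit with one unit, identically in the synopsis and in section 5.2.2.
3. Make section 8.5 agree with exclusion criterion 3.

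The choice in each case is the sponsor's clinical decision. The cost is amendment text in the synopsis and sections 2.2, 5.2.2 and 8.5, plus matching changes to any screening documents. Design, sample size and primary analysis stay as they are. The effect on the number of eligible patients depends on the choices made and cannot be estimated from the protocol.
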